5.5.2 Antibodies (ADA)

Serum will be analysed for ADA formation to rVA576 (Coversin), as per schedule of events and stored and shipped frozen for analysis.

5.5.3 LTB4

Plasma (EDTA-treated) will be collected as per Schedule of Events and stored and shipped frozen for analysis.

5.5.4 LDH Isoenzymes

The assay determines the absolute LDH value and the proportions of LDH Isoenzymes 1 to 5. The serum sample should be stored and shipped to The Doctors Laboratory (TDL) at ambient temperature immediately. Do not store samples at 2-8°C. Do not use frozen or haemolysed samples.

5.5.5 Total C5 Levels

C5 is the complement protein bound by rVA576 (Coversin). C5 concentration in blood will be measured by ELISA to understand how and if individual subject levels of C5 vary through time. Serum samples used should be stored and shipped frozen prior to analysis.

5.5.6 Fluorescein-labelled proaerolysin FLAER / Flow Cytometry

FLAER accurately determines the number and proportion of white blood cells that lack GPI-anchor and therefore lack the complement regulatory proteins CD55 and CD59.

The whole blood EDTA sample is analysed from an ambient temperature sample. Flow cytometry using anti-CD55 and anti-CD59 antibodies identifies the number and proportion of red blood cells deficient in these GPI-linked proteins. Absence of CD55 and CD59 are

diagnostic for PNH. Clone size (proportion of cells affected) can change through time and with C5 inhibition.

5.5.7 Central Laboratory Testing (if not done within 14 days of entry)

LTB4	Anti-Drug Antibody (ADA)
CH50	rVA576 Level (PK)
C5	LDH Isoenzyme
C3 (aHUS only)	

If any site is unable to use the standard laboratory kits provided by the Central Laboratory, the site needs to inform the Sponsor immediately (providing justification) as it may have an impact on the analysis of samples and ultimately the study results.

5.5.8 Pharmacokinetics (PK) and Pharmacodynamics (PD) (aHUS only)

Blood samples for PK and PD will be collected as detailed in the schedule of events. Samples for PK and PD will be taken 5 – 60 minutes before IMP administration. The date and exact time of collection must be recorded.

The sample for PK/PD (CH50) analysis may be taken prior and/or after plasma exchange and/or dialysis. As the CH50 results are unlikely to be available for some days, the Investigator should be guided by the history, clinical signs or Platelet count and LDH as to whether it is necessary to administer additional Ablating Doses. Clinical signs of intravascular haemolysis following resumption of dosing mandates re-initiation of the Ablating dose schedule. The CRO and the Sponsor should be informed as soon as possible.

5.6 Efficacy Assessments

Measures of clinical efficacy will be assessed by the Investigator. The Sponsor (or designee) will review all eCRFs regularly for all patients in the study.

Details of safety and efficacy endpoints are detailed in section 3.2.1

5.7 Safety Assessments

5.7.1 Medical History and Present Conditions

A complete medical history will include an evaluation of the previous medical history from the previous rVA576 (Coversin) trial which will be transferred to the current database.

As all patients enrolled into the CONSERVE study will have transitioned from a parent clinical trial, a full new medical history and examination is not considered necessary unless there has been a lag time in entry into the long term study. The investigator responsible for the patient's treatment will decide if there have been significant changes in the patient's condition since being in the previous study to warrant an additional examination and new entries to the medical history page. If there has been development of a new medical condition (with diagnosis) in the previous study this will be considered as part of the patient's medical history for this study.

Plasma Transfer/Dialysis History is also required for aHUS patients.

Relevant data held in databases from previous rVA576 (Coversin) trials will be transferred to the current database in pdf format.

5.7.2 Physical Examination (if not done within 7 days of entry)

- General appearance
- Dermatological / skin
- Haematologic / lymphatic
- Heart / cardiovascular
- Respiratory
- Vein and injection site inspection

5.7.3 Vital Signs & Weight

Blood pressure and pulse rate will be measured in the supine position after the patient has rested comfortably. Body weight will be recorded, if not done within 14 days of entry. Measurements will be recorded in the patient's eCRF.

5.7.4 Cardiac Safety

Routine ECG should be performed at entry and then annually during the study. The ECG traces (*using Limb lead or 12 lead ECG depending on what is available at site*) will be reviewed, signed, and dated by a physician and he/she will record on the trace whether the ECG is normal or abnormal and if deemed abnormal, whether the abnormality is clinically significant (CS) or not clinically significant (NCS).

5.7.5 Clinical Laboratory Safety Tests (if not done within 14 days of entry)

All samples will be collected in accordance with acceptable laboratory procedures at the time points specified in the Schedule of Events **Table 8 & Table 9**. Additional and repeat testing may be performed at the discretion of the Investigator. All clinical laboratory safety tests will be performed locally by each clinical unit unless this is not possible in a participating country.

Baseline haematology, chemistry and urinalysis will be performed at entry unless these investigations have taken place within 14 days of screening.

5.7.6 Major Adverse Vascular Event (MAVE) Assessment

The MAVE will be used to collect information on large and small vessel thrombosis as well as micro thrombosis and will be recorded always pre-dose at each clinic visit.

5.7.7 Pregnancy Test

Pregnancy tests for women of childbearing potential (WOCBP) must be done monthly. The current protocol design requires a urine pregnancy test at entry and at each clinic visit. In addition, home pregnancy tests must be repeated every month during the use of rVA576 (Coversin) and up to 90 days after the last dose of rVA576 (Coversin) by the patient.

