5.4 Trial procedures**5.4.1 Screening**

Patients considered unsuitable for inclusion in this trial should be identified by their Investigator before the end of their participation in the preceding trial (i.e. should the investigator feel participation in the long term safety study is not in the patient's benefit or if the patient declines to participate in AK581) allowing adequate time for any alternative therapy to be implemented. The Investigators should discuss the suitability of patients to enter AK581 with the Sponsor at least four weeks before the likely time of entry in order that documentation, including ICF, can be put in place and continuity of drug supply can be ensured.

Ideally the patient will be entered on the long term safety trial on the last day of dosing of the parent trial on condition that they have provided consent.

5.4.2 *Dosing period(s)*

Patients will be dispensed drug at suitable timepoints during the trial

5.4.3 *Exiting the trial*

Patients may choose to leave the trial at any time or may be withdrawn by the Investigator in case of lack of efficacy, adverse reactions to rVA576 (Coversin), lack of compliance or for any other reason which, in the opinion of the Investigator, makes their continued participation no longer in their best interests.

Patients will also leave this trial, or an extended access trial if one is required, once rVA576 (Coversin) is fully approved and reimbursed for their indication in their country and once continuity of supply has been ensured.

5.4.4 *End of Study/Follow-up*

All patients will have a follow up clinic visit at 1 Month \pm 7 days and all women of child bearing potential (WOCBP) will have a follow up visit at Month 3 \pm 7 days from last dose.

Table 8: Schedule of Events for PNH Patients

EVENT (PNH)	Entry	ⁱ 1 Months (±7 days)	2 Months (±7 days)	3 Months (±7 days)	6 Months (±7 days)	9 Months (±7 days)	12 Months (±7 days)	15 Months (±7 days)	18 Months (±7 days)	21 Months (±7 days)	24 Months (±7 days)
Medical History. Eligibility & Informed Consent & demographics	✓										
ⁱⁱⁱ Physical Examination if not done within 7 days of entry	✓	✓	✓	✓	✓	✓	✓	✓	✓	✓	✓
^{iv} Vital Signs (including weight) at every visit	✓ ^{vii}	✓	✓	✓	✓	✓	✓	✓	✓	✓	✓
^v ECG	✓ ^{vii}						✓				✓
Urinalysis (including pregnancy testing) ^{viii}	✓ ^{vii}	✓	✓	✓	✓	✓	✓	✓	✓	✓	✓
ⁱⁱ Haematology & Chemistry including LDH, FBC and creatinine (local or central labs)	✓ ^{vii}	✓	✓	✓	✓	✓	✓	✓	✓	✓	✓

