AE and Concomitant Medication reporting	✓	✓	✓	✓	✓	✓	✓	✓	✓	✓
MAVE Assessment	✓	✓	✓	✓	✓	✓	✓	✓		✓

Table 8 Notes (for PNH patients):

- i. Investigator visits may take place more frequently if needed or desired (unscheduled visits/testing where needed), but the schedule shown is the minimum permitted
- ii. All blood draws will be taken pre-dose. If not possible, a note to that effect must be made in the medical records and captured in the eCRFs
- iii. Physical Examination - Inclusive of vein assessment and injection site inspection
- iv. Vital Signs – Diastolic and Systolic blood pressure & pulse rate
- v. Patients must complete the Quality of Life (QOL) Instruments and sponsor non-validated questionnaire at every clinic visit
- vi. Drug accountability will be performed at each visit. Patients are requested to bring in empty vials only and inform the site of unused vials remaining in their fridge.
- vii. Test to be conducted at entry if not done within 14 days of entry visit.
- viii. Pregnancy tests for women of childbearing potential must be done monthly. The current protocol design requires a pregnancy test at each hospital visit and then every 3 months after Month 3 (Months 1, 2, 3, 6, 9, 12, 15, 18, 21, 24, 27, 30, 33, 36, 39, 42, 45, 48 & ET). In addition Home Pregnancy tests must be repeated every month during the use of rVA576 (Coversin) and up to 90 days after the last dose of rVA576 (Coversin) by the patient.
- ix. Total LDH and LDH isoenzymes via a central laboratory maybe required as per the schedule to monitor patient safety (unscheduled visit/test is also permitted)
- x. All patients will have a follow up clinic visit at 1 Month ± 7 days in addition all women of childbearing potential (WCBP) will have a follow up visit at Month 3 ± 7 days from last dose whereby urine pregnancy test will be conducted on site.
- xi. Routine ECG to be performed at entry and then annually during the study. (*Limb lead or 12 lead ECG machines are acceptable*)

FLAER/Flow Cytometry: Local lab or via Central Lab (if not available locally). A 7 day window is permitted for each visit.

Table 9: Schedule of Events for aHUS patients

EVENT (aHUS)	Entry	ⁱ 1 Months (±7 days)	2 Months (±7 days)	3 Months (±7 days)	6 Months (±7 days)	9 Months (±7 days)	12 Months (±7 days)	15 Months (±7 days)	18 Months (±7 days)	21 Months (±7 days)	24 Months (±7 days)
Medical History, Eligibility, Informed Consent & demographics	✓										

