5.7.8 Additional Investigational & Safety Testing

Additional, non-genetic testing may be conducted on retained samples if deemed appropriate by the Investigator or should additional research suggest further investigation is required to improve disease evaluation and drug response. Consent for additional, currently undetermined, exploratory analysis will be in place prior to further analysis. The patient may refuse additional testing on their retained samples at any point and this will not influence their participation in the study.

Additional and repeat blood draws considered necessary for safety and well-being of the patient may be performed at the discretion of the Investigator.

Further to the above, the Sponsor and Investigator may request additional blood samples, (not listed in the Schedule of Events), to be taken during the course of the study to support further non-genetic testing, should there be insufficient blood remaining in the retained sample. A maximum study blood draw volume of 800mL per patient will not be exceeded inclusive of additional testing.

Additional, currently undetermined, exploratory analysis is likely to be done for C3, C3a, C5a and sC5b9.

Haematology Parameters

White blood cell count	Neutrophils absolute
Red blood cell count	Lymphocytes absolute
Haemoglobin	Monocytes absolute
Mean Cell Haemoglobin (MCH)	Mean Cell Haemoglobin Concentration (MCHC)
Haematocrit	Eosinophils absolute
Erythrocyte sedimentation rate (ESR)	Basophils absolute
Platelets	Mean Cell Volume (MCV)
Reticulocytes	

Chemistry Parameters

Lactate dehydrogenase & LDH isoenzymes	Glucose (Random)
Sodium	Alkaline phosphatase
Potassium	Alanine Aminotransferase (ALT)
Bicarbonate	Aminotransferase (AST)
Urea	Creatine Kinase (CK)
Creatinine	Total Bilirubin
Chloride	Bilirubin (Direct) (only if Total is elevated)
Albumin	Phosphate (Inorganic)
Calcium	Protein (Total)
Gamma Glutamyl Transpeptidase (GGT)	

Urinalysis Parameters

Leukocytes	Ketones
Protein	Nitrates
Bilirubin	Blood
Glucose	hCG (female WOCBP patient)
pH	Specific gravity
At Discretion of PI Based on Urinalysis Results Microbiology Urine Microscopy Pregnancy testing	Urobilinogen

5.8 Data that can be carried over from previous study to current AK581 study:

If done within 7 days of entry:

- Physical exam & QOL

If done within 14 days of entry:

- CH50 + complement factors and activation markers, rVA567 level (PK), LTB4, Haematology, Chemistry, Urinalysis.

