If ECG, vital signs, Pregnancy testing and MAVE are done on the same day as the end of study visit for the previous study as the entry day for the long term safety study, then these procedures do not need to be repeated again.

Note: laboratory results can only be used if they are from the same reference laboratory in both studies.

aHUS Parameters

If done within 14 days of entry:

- Thrombotic Markers (D-dimer, prothombin f1/f2)
- Pro-inflammatory Markers (platelet E and P-selectin, CRP (high-sensitivity))
- Haemolytic Markers (Haptoglobin)
- Schistocyte count
- Dialysis Assessment & Plasma Transfer record

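### Table 8 note vii waives the entry pregnancy test after a test 1 to 14 days earlier, but 5.7.7 requires one at entry and 5.8 excuses only a same-day test

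*Protocol*

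**What the plan says.** The entry pregnancy test is governed from several places in the protocol.

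- **5.7.7:** "The current protocol design requires a urine pregnancy test at entry and at each clinic visit". No window is attached.
- **Table 8:** pregnancy testing has no row of its own. It shares one labelled "Urinalysis (including pregnancy testing" (the label closes its bracket there). The Entry tick in that row carries note vii: "Test to be conducted at entry if not done within 14 days of entry visit".
- **Table 8 note viii:** covers the timing of pregnancy tests, but its visit list starts at Month 1 and does not name Entry.
- **5.8, 14-day list:** the items that may be carried over end with "rVA567 level (PK), LTB4, Haematology, Chemistry, Urinalysis". Pregnancy testing is not named.
- **5.8, same-day sentence:** a separate sentence opens "If ECG, vital signs, Pregnancy testing and MAVE are done on the same day as the end of study visit for the previous study" and, where that day is also the entry day, excuses a repeat.
- **Urinalysis parameters (table before 5.8):** the panel includes "hCG (female WOCBP patient" (bracket again closed in the original).
- **5.7.5:** the heading reads "Clinical Laboratory Safety Tests (if not done within 14 days of entry", closing its bracket, while the body says "Baseline haematology, chemistry and urinalysis will be performed at entry unless these investigations have taken place within 14 days of screening".

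On eligibility, inclusion criterion 4 asks for a negative test at screening, exclusion criterion 5 bars pregnancy, and SAP 3.2.3 has the criteria assessed at Entry. Section 7.2.4 contraindicates the drug in pregnancy. Table 9 repeats the row and note vii for aHUS, but SAP section 1 says that no aHUS patients will enter.

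**The concern.** A coordinator working from the schedule table may accept a parent-trial pregnancy test from the previous two weeks and do none at entry. A monitor working from 5.7.7 would find a required test missing at that same entry. With the 100% source data verification planned in sections 8 and 10, the discrepancy is likely to surface, and it concerns an eligibility item.

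This matters more than a stale baseline value would. The drug must be stopped in pregnancy unless the patient consents to a termination (7.2.4), and 4.6 says that segment 2 and 3 reproductive toxicology studies are still to be done. Same-day rollover is described in 5.4.1 only as the ideal. Section 5.7.1, although it deals with medical history, foresees a lag before entry in some cases, and the 7- and 14-day carry-over windows in 5.8 would serve no purpose if every patient crossed over on one day.

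**Working it through.** The plan states no figure on this point to reproduce. The check sets the rules side by side by the age of the last parent-trial pregnancy test on the day of entry.

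| Age of test at entry | Table 8 note vii | 5.7.7 | 5.8 same-day sentence |
|---|---|---|---|
| 0 days | waived | met by that day's test | repeat excused |
| 1 to 14 days | waived | test required | not excused |
| more than 14 days | test required | test required | not excused |

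**Step 1, the conflict.** The three rules agree in the first and third lines and disagree in the second. The 5.8 sentence does not contain the word only; that it is limited to the same day follows by implication. If a 14-day carry-over already covered pregnancy testing, naming it there would be redundant.

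**Step 2, can note viii settle it?** No. Its list begins at Month 1. Reading Entry into its general reference to hospital visits would put notes vii and viii in conflict within Table 8.

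**Step 3, the urinalysis waivers.** hCG is a urinalysis parameter, so the 14-day carry-over of urinalysis in 5.8 can be read as covering the pregnancy test. On that reading 5.8 disagrees with itself, and 5.7.7 still has no window. Section 5.7.5 adds a second difficulty: its heading counts 14 days from entry and its body from screening. If screening precedes entry and hCG is read into urinalysis, the body could excuse a test more than 14 days old at entry. The third line of the table therefore holds for the three rules shown, but not securely for 5.7.5.

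**Step 4, how many rows.** Table 8 Entry ticks with note vii are:

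1. vital signs
2. ECG
3. urinalysis with pregnancy testing
4. haematology and chemistry
5. CH50, PK and LTB4
6. ADA
7. total LDH and isoenzymes
8. total C5
9. FLAER or flow cytometry

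The 5.8 same-day sentence names ECG, vital signs, pregnancy testing and MAVE. The MAVE Entry tick has no note vii. The overlap is ECG, vital signs and pregnancy testing: 3 of 9 rows.

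**Step 5, the cause.** ECG and vital signs have rows of their own and show the same 14-day versus same-day mismatch. The common cause is that note vii was not aligned with 5.8. Placing the pregnancy test in the urinalysis row adds to the problem but does not by itself explain it.

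**The case against.** The strongest reply is that the protocol can be followed as it stands. Note vii permits omission but does not forbid testing, so a test on the entry day satisfies every passage. A specific rule for pregnancy testing in 5.8 would also normally prevail over a general footnote. Both remarks are fair, but they show only how a careful site could avoid the problem. A site that uses the waiver printed in the schedule still misses what 5.7.7 requires.

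It can also be said that adding a 14-day allowance to 5.7.7 and 5.8 would remove the contradiction equally well. As a matter of consistency that is true. The stricter direction is preferable because the two passages that name the pregnancy test at entry both point that way and because it costs little, not because the lenient rule has been shown to be unsafe.

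Three stronger readings are tempting, and the documents do not support them.

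- **A reader might infer a gap in pregnancy surveillance.** The waiver lengthens one interval between clinic tests by at most 14 days. After Month 3 the clinic visits are themselves three months apart. Taking months of 30 to 31 days and the ±7 day windows, an early Month 3 visit and a late Month 6 visit are 3 × 30 + 14 = 104 to 3 × 31 + 14 = 107 days apart. Monthly home tests cover such intervals, so no detection benefit can be claimed.
- **A reader might infer that women would be entered in breach of inclusion criterion 4.** That criterion refers to screening, and SAP 3.2.3 sets no maximum age for a test. A carried-over negative test need not breach it.
- **A reader might infer that entry starts fetal exposure.** Patients come from a parent trial already on the drug, and 4.6 requires contraception from consent.

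**Conclusion.** Wrong as written, minor. For women of childbearing potential whose last parent-trial test was 1 to 14 days before entry, note vii and 5.7.7 cannot both describe what the site must do, and 5.8 leans towards 5.7.7. The urinalysis waivers in 5.8 and 5.7.5 add ambiguity. Of the three mismatched rows, the pregnancy test matters most because it bears on eligibility and the drug is contraindicated in pregnancy.

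The safety gain from correcting it is small, and none of the planned descriptive summaries would change. The size of the affected group cannot be stated, because the documents do not say how many women enter with such a gap; if all roll over on the same day, it is none. The conclusion rests on reading note vii as applying to the whole row in which the pregnancy test sits, and on reading the 5.8 sentence as limiting the excuse to the day of entry.

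**What to change.** 1. In Table 8, keep note vii on urinalysis and add a separate row for the urine pregnancy test in women of childbearing potential, with an Entry tick and no note vii. State that it is done on the entry day unless a parent-trial test was done that same day. Mirror this in Table 9 for consistency.
2. In 5.8, exclude hCG from urinalysis in the 14-day list.
3. In 5.7.5, exclude hCG from the 14-day waiver, and count the 14 days from entry in both heading and body.
4. In the same edit, align note vii with 5.8 for ECG and vital signs. Weight shares the vital signs row and has its own 14-day allowance in 5.7.3, so it can keep that.
5. Optionally, change screening to entry in inclusion criterion 4. This is a matter of terminology and the correction does not depend on it.

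Section 5.7.7 can stay as it is. The cost is amendment wording and, for women with a 1 to 14 day gap, one urine test at a visit they already attend. If ECG and vital signs are aligned to the same-day rule, patients with such a gap would also have those repeated at entry, as 5.8 already implies.

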5.7.8 Additional Investigational & Safety Testing

Additional, non-genetic testing may be conducted on retained samples if deemed appropriate by the Investigator or should additional research suggest further investigation is required to improve disease evaluation and drug response. Consent for additional, currently undetermined, exploratory analysis will be in place prior to further analysis. The patient may refuse additional testing on their retained samples at any point and this will not influence their participation in the study.

Additional and repeat blood draws considered necessary for safety and well-being of the patient may be performed at the discretion of the Investigator.

Further to the above, the Sponsor and Investigator may request additional blood samples, (not listed in the Schedule of Events), to be taken during the course of the study to support further non-genetic testing, should there be insufficient blood remaining in the retained sample. A maximum study blood draw volume of 800mL per patient will not be exceeded inclusive of additional testing.

Additional, currently undetermined, exploratory analysis is likely to be done for C3, C3a, C5a and sC5b9.

Haematology Parameters

White blood cell count	Neutrophils absolute
Red blood cell count	Lymphocytes absolute
Haemoglobin	Monocytes absolute
Mean Cell Haemoglobin (MCH)	Mean Cell Haemoglobin Concentration (MCHC)
Haematocrit	Eosinophils absolute
Erythrocyte sedimentation rate (ESR)	Basophils absolute
Platelets	Mean Cell Volume (MCV)
Reticulocytes	

Chemistry Parameters

Lactate dehydrogenase & LDH isoenzymes	Glucose (Random)
Sodium	Alkaline phosphatase
Potassium	Alanine Aminotransferase (ALT)
Bicarbonate	Aminotransferase (AST)
Urea	Creatine Kinase (CK)
Creatinine	Total Bilirubin
Chloride	Bilirubin (Direct) (only if Total is elevated)
Albumin	Phosphate (Inorganic)
Calcium	Protein (Total)
Gamma Glutamyl Transpeptidase (GGT)	

Urinalysis Parameters

Leukocytes	Ketones
Protein	Nitrates
Bilirubin	Blood
Glucose	hCG (female WOCBP patient)
pH	Specific gravity
At Discretion of PI Based on Urinalysis Results Microbiology Urine Microscopy Pregnancy testing	Urobilinogen

5.8 Data that can be carried over from previous study to current AK581 study:

If done within 7 days of entry:

- Physical exam & QOL

If done within 14 days of entry:

- CH50 + complement factors and activation markers, rVA567 level (PK), LTB4, Haematology, Chemistry, Urinalysis.

If ECG, vital signs, Pregnancy testing and MAVE are done on the same day as the end of study visit for the previous study as the entry day for the long term safety study, then these procedures do not need to be repeated again.

Note: laboratory results can only be used if they are from the same reference laboratory in both studies.

aHUS Parameters

If done within 14 days of entry:

- Thrombotic Markers (D-dimer, prothombin f1/f2)
- Pro-inflammatory Markers (platelet E and P-selectin, CRP (high-sensitivity))
- Haemolytic Markers (Haptoglobin)
- Schistocyte count
- Dialysis Assessment & Plasma Transfer record

